January 2nd 2023

Effect of Biologics on Alternative Functions of Eosinophils in Severe Asthma

EudraCT: NCT04520165

Scientific Background and goal

Refractory asthma still represents between 3 to 10% of asthmatic patients. These patients represent a high burden in terms of healthcare costs. Biotherapies have been developed within the last years to reduce the use of oral corticosteroids (OCS), which are responsible for long-term and costly side effects. Monoclonal antibodies directed against interleukin (IL)-5 or its receptor (IL-5R) are approved to treat severe eosinophilic asthma with tangible improvements of the patient conditions. But it appears that the patients do not respond the same way to biotherapies.

In addition to the “super-response”, a new concept of asthma “remission” has recently emerged as a therapeutic target to achieve after 12 months of treatment and was defined according to results of randomized control trials (RCT) as obtaining asthma control, no exacerbation, no treatment with OCS while there is no consensus on the importance of improvement in lung function and reduction in type-2 (T2) inflammation in the current definition of remission.

Post-hoc analysis of RCT looked at the predictive factors of response to benralizumab or mepolizumab in vast cohorts of patients and observed that high blood eosinophil level was linked to a better improvement in terms of reduction of exacerbation rate. Even if blood eosinophils help to predict a general response to anti IL-5/ anti IL-5R, biomarkers reflecting local inflammation, such as those measured in induced sputum, have a better potential to predict the intensity of response to biologics as they reflect what really happens in the bronchi. So are there biomarkers of remission after therapy targeting IL-5 in the sputum of severe eosinophilic asthmatics? There are, to our knowledge, no studies analyzing inflammatory mediators as predictors of response after one year of anti-IL-5 treatment directly in the sputum itself in severe eosinophilic asthmatics. The goal of this paper is to analyze the role of mediators of the T2 cascade in the sputum as predictors of remission.

Study design and methods

Patients

Fifty-two severe asthmatics initiated with an anti-IL-5 (51 with Mepolizumab and one with Reslizumab) were recruited from our asthma clinic. This observational study was performed at the CHU of Liege, Belgium, between 2014 and 2021. Inclusion criteria included a diagnosis of asthma defined by the Global Initiative for Asthma (<http://ginasthma.org/>), severe asthma was defined according to European Respiratory Society (ERS)/ American Thoracic Society (ATS) criteria. The treatment was stable for all patients at the time of the sampling and the time between baseline and the next evaluation was in average one year. Remission was defined as patients combining after the instauration of the biotherapy: no oral corticosteroids, no exacerbation, ACQ lower than 1.5 and/or asthma control test (ACT) greater than 19 and, a FEV₁ \geq 80% predicted and/or an improvement of FEV₁ \geq 10% and a blood eosinophil count lower than 300 cells/ μ l.

Sub-analyses were also performed to assess the predictive values of sputum mediators in terms of response for some specific parameters alone, such as: an improvement of ACT greater than 19 post-treatment, a decrease of ACQ lower than 1.5 post-treatment, a decrease of sputum eosinophil under 3% or by 50%, stopping OCS post-treatment, no more exacerbations post-treatment and improvement of FEV₁ of at least 10% post-treatment.

A diagnosis of nasal polyps by an Ear-Nose-Throat specialist and a diagnosis of atopic dermatitis or urticaria done by a dermatologist were reported.

This study was approved by the Ethics committee of CHU Liege (2005/181) and all subjects gave written informed consent for participation. The study ClinicalTrials.gov Identifier is clintrial.org EudraCT: NCT04520165.

Study design

This study aims to investigate the airway expression of mediators of the T2 cascade as predictors of remission after anti-IL-5 treatment in a cohort of patients with severe eosinophilic asthma. To detect a difference between groups with a power of 70-80% and a significance level of 5%, the sample size was estimated as 10-13 patients per group (<https://www.sealedenvelope.com/>). These calculations were based on a significant difference of sputum IL-5 obtained as preliminary results. Usually, in the different studies, even if there is no consensus on the remission definition in the asthma context, there is mention of a percentage around 20% of patients exhibiting a good response to anti-IL-5. Consequently, with a cohort of 52 patients, we expected a sample size of at least 10 patients in the remission group.

Respiratory function

FeNO was measured using NiOX (Aerocrine, Solna, Sweden) at a flow rate of 50 mL/s. Spirometry was performed before and after bronchodilation according to the ATS/ERS standard criteria.

Blood samples

Blood samples of patients were analyzed by the routine laboratory of the University Hospital of Liege for leukocyte count, c reactive protein (CRP) and fibrinogen levels.

Sputum induction and processing.

The sputum was induced and processed as previously described and the sputum supernatant was collected before the addition of dithiothreitol (DTT), which could impact the measurements. Cell viability was determined by trypan blue exclusion and the differential cell count was performed by counting 500 non-squamous cells on cytospins stained with May-Grünwald-Giemsa.

Sputum inflammatory mediators measurement

Eosinophil peroxidase (EPX) was measured by classic ELISA (Mybiosource, CA, USA). Detection limit was 5.4 ng/ml. Immunoglobulin E (IgE) levels were measured with Human IgE ELISA kit from Abcam (Amsterdam, Netherlands). The detection limit was 30.5 pg/ml. Finally, interleukin (IL)-3, IL-4, IL-5, IL-13, IL-25, IL-33, granulocyte-macrophage colony-stimulating factor (GM-CSF), thymic stromal lymphopoitin (TSLP) and eotaxin-1 were measured by multiplex electrochemiluminescent assays (Meso Scale Discovery). This technic was already used with success in sputum supernatant in the past and spiking recovery were optimal.

Statistical analysis

Categorical variables are presented as numbers and percentages, continuous variables are presented as mean \pm standard deviation or as median (interquartile range P25-p75) when appropriate.

The normality of continuous variables was assessed by Shapiro-Wilk test (normal distribution was found for age, BMI, ACQ, AQLQ, pulmonary function parameters, fibrinogen level, and sputum neutrophil percentage). To investigate baseline characteristics of patients remission group, Chi-square or Fisher exact test was used for categorical variables and Student t test or Mann-Whitey U test was performed for continuous variables when appropriate.

Univariate logistic regression was considered to model the association between patient remission status and demographic, clinical and biological variables. Results of logistic regression were presented using odds ratios and corresponding 95% confidence interval.

All tests were performed 2-sided and $p < 0.05$ was considered significant. All statistical analyses were performed using SAS 9.4 (SAS Institute, Cary, NC), except for ROC curve calculation, GraphPad Prism 7 (GraphPad Software San Diego, CA, USA) was used. The p-values associated with the ROC curves tested the null hypothesis that the area under the curve equals 0.50.

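### The remission-group size is an expected count stated as a minimum, and the 70-80% power is for equal groups, not for remitters against the rest of the 52

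*Combined protocol and SAP*

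**What the plan says.** The sample-size reasoning is in the Study design section of the combined protocol and SAP.

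- **Requirement.** The section sets the target "with a power of 70-80% and a significance level of 5%, the sample size was estimated as 10-13 patients per group". The basis is given as "These calculations were based on a significant difference of sputum IL-5 obtained as preliminary results". Neither the size of that difference nor its SD appears.
- **Rate.** After conceding that remission has no agreed definition, the section says of other studies that "there is mention of a percentage around 20% of patients exhibiting a good response to anti-IL-5". It does not define a good response.
- **Conclusion.** "Consequently, with a cohort of 52 patients, we expected a sample size of at least 10 patients in the remission group".

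The Patients section defines remission as five conditions met together: off oral corticosteroids, free of exacerbations, control by ACQ or ACT, an FEV1 criterion, and blood eosinophils under 300 cells per microlitre. The Scientific Background section describes remission by the first three and says that the place of lung function and T2 inflammation is not settled.

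The Statistical analysis section compares patients by remission status, using a t test or Mann-Whitney test for continuous variables. It says "All tests were performed 2-sided", with p < 0.05 as the threshold.

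**The concern.** Three steps in the reasoning do not connect.

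1. A rate multiplied by a cohort size gives an average count. Calling it a minimum removes the sampling variation. Ten is also only the lower end of the 10-13 requirement, the end that goes naturally with 70% power.
2. The rate is not shown to be a rate for the outcome analysed. A reader cannot tell whether 20% refers to the five-part definition, to a three-part one, or to something else.
3. A per-group figure reads as equal groups. The analysis sets the remitters against everyone else in the 52, roughly 10 against 42, which has different power.

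The number of remitters governs the precision of the group comparisons, the logistic regressions and the ROC curves. A reader who takes the group size and the power at face value has the wrong figure for each.

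**Working it through.** **Inputs.** From Study design: N = 52, rate about 20%, 10-13 per group, power 70-80%, alpha 5%. From Statistical analysis: two-sided tests. Not given: the preliminary IL-5 difference, its SD, and any remission rate for the five-part definition. Rates of 15% and 10% below are assumptions, used only to show sensitivity.

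**Step 1: reproduce the plan's figure.** 52 x 0.20 = 10.4. The 10 is reproduced, as a mean.

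**Step 2: chance of reaching the target.** With R ~ Binomial(52, p), P(R >= k) is the sum over j = k to 52 of C(52, j) p^j (1-p)^(52-j).

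| True rate | Mean | P(R >= 10) | P(R >= 13) | P(R <= 5) |
|---|---|---|---|---|
| 20% (plan) | 10.4 | 61% | 23% | 4% |
| 15% (assumed) | 7.8 | 25% | 4% | 19% |
| 10% (assumed) | 5.2 | 3% | 0.1% | 58% |

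At 20% the 2.5th and 97.5th percentiles of R are 5 and 16. The chance of fewer than 10 is 100% - 61% = 39%. For an 80% chance of at least 10 among 52, the true rate would have to be about 23%.

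**Step 3: effect implied by 10-13 per group.** I pair 10 with 70% and 13 with 80%, and assume a two-sided comparison of two means. With the normal formula, d = (z for alpha/2 + z for power) x sqrt(2/n):

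- n = 10, 70%: (1.960 + 0.524) x sqrt(0.2000) = 1.11
- n = 13, 80%: (1.960 + 0.842) x sqrt(0.1538) = 1.10

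Solving with the exact t distribution instead gives 1.17 and 1.15. I use 1.10 to 1.18 SD as the range. The two ends of the plan's requirement agree with each other.

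**Step 4: power for the actual split.** For a t test of r against 52-r, the noncentrality is d / sqrt(1/r + 1/(52-r)) on 50 degrees of freedom. For 10 v 42 the divisor is sqrt(0.1000 + 0.0238) = 0.352, so the noncentrality is 3.1 to 3.4. For 10 v 10 the divisor is sqrt(0.2000) = 0.447. The larger comparison group is where the extra power comes from.

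| Split | Power, d = 1.10 to 1.18, two-sided 5% |
|---|---|
| 13 v 39 | 92-95% |
| 10 v 42 | 87-91% |
| 8 v 44 | 80-85% |
| 6 v 46 | 70-76% |
| 5 v 47 | 63-69% |

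**Step 5: average over the unknown count.** Weighting power at each r by its binomial probability (normal formula, d = 1.105) gives 87% at a 20% rate, 78% at 15% and 63% at 10%.

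**Sensitivity.** Sputum IL-5 is not among the variables listed as normally distributed, so the Mann-Whitney test may apply. Multiplying the sample size by an efficiency factor of 0.955 takes 10 v 42 at d = 1.105 from 88% to 87% by the normal formula, a negligible change.

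**The case against.** The best defence is that this is loose wording with little consequence. The plan says the number was expected and the rate approximate, the arithmetic behind 10 reproduces, and 10-13 for the smaller group is a cautious requirement when the other group has about 42. Recruitment is over, so no sample-size decision remains. Most of this stands. It does not rescue the minimum: an expectation of 10.4 leaves a 39% chance of falling short of 10 even if the rate is right.

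Three stronger readings are tempting, and the documents do not support them.

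- **That the study is underpowered for IL-5.** At the implied effect, the expected split gives more power than stated, and 6 to 8 remitters still give about 70-85%. Power falls below 70% only at about 5 or fewer remitters, a 4% chance at the plan's rate.
- **That the 20% is known to come from an easier outcome.** The same sentence refers to the remission definition, so good response may be loose wording for remission. The control and FEV1 conditions also allow alternatives. What can be said is that the 20% is not tied to the five-part definition.
- **That power must be judged at a level corrected for the 11 sputum mediators.** The plan states no such correction, and its calculation is for IL-5 alone at 5%. Multiplicity is a separate question.

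**Conclusion.** The point holds in a limited form. The minimum of 10 is a mean of 10.4, reached or exceeded with probability 61% at a true 20% rate, with a 95% range of 5 to 16. The rate is not shown to apply to the outcome analysed; if it were 15% or 10%, the chance of at least 10 would be 25% or 3%. The stated 70-80% power does not describe the comparison made: at the expected split it is too low (about 87-91%), and it is missed only with about 5 or fewer remitters. That count becomes likely (58%) only if the true rate is as low as the assumed 10%.

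The power figures rest on an effect of 1.10-1.18 SD inferred from the plan's group sizes, because the plan does not state one. They would fall if the preliminary IL-5 difference was optimistic. They also assume usable baseline sputum and outcome data for all 52; the plan makes no allowance for missing samples.

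**What to change.** In Study design:

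1. Replace the minimum with *about 10 (95% range 5-16 at a 20% rate)* or, better, with the observed number in remission. The study ran from 2014 to 2021 and the document is dated January 2023, so that number should be available.
2. Say which outcome definition the 20% refers to, and whether it matches the five-part remission.
3. State the preliminary sputum IL-5 difference and its SD.
4. Restate power for r against 52-r over r = 5 to 13, and note that it covers IL-5 alone at a two-sided 5%.

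The cost is restated figures only: no extra patients and no change of analysis. The power statement becomes conditional on the number of remitters.

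### With about 10 remitters against 42 others, Student's t test does not hold its 5% level if the spreads differ; Welch's test does, at a modest cost in power

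*Combined protocol and SAP*

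**What the plan says.** The Statistical analysis section describes the comparison of the remission group with the remaining patients at baseline. For continuous variables, "Student t test or Mann-Whitey U test was performed for continuous variables when appropriate". The same section reports a Shapiro-Wilk check and its result: "normal distribution was found for age, BMI, ACQ, AQLQ, pulmonary function parameters, fibrinogen level, and sputum neutrophil percentage". No sputum mediator is on that list. The section names no check of equal variances and no unequal-variance version of the t test. Tests are two-sided at 0.05, and confidence intervals are promised only for odds ratios.

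The group sizes come from two places. The Patients section gives the total: "Fifty-two severe asthmatics initiated with an anti-IL-5". The Study design section cites a good-response share of around 20% and concludes that "we expected a sample size of at least 10 patients in the remission group".

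**The concern.** Student's t test estimates one common SD from both groups. When one group is about four times the size of the other, that estimate is mostly the larger group's SD. The uncertainty of the difference in means, however, comes mostly from the smaller group. If remitters vary more than the others, the standard error is too small and the test rejects too often. If they vary less, it is too large and the test rejects too seldom. A normality check cannot reveal this.

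At stake is the reading of the baseline comparison for age, BMI, ACQ, AQLQ, lung function, fibrinogen and sputum neutrophil percentage. A characteristic might be called different between the groups, or not, at an error rate that is not the stated 5%.

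**Working it through.** **Inputs.** Total 52 (Patients). Remission share about 20%, at least 10 remitters expected (Study design). Two-sided 0.05 (Statistical analysis). Not given in the documents: group SDs and any effect size. Assumed here: normal data, SD ratios r (remitters/others) from 0.5 to 2, and standardised differences d from 0.8 to 1.2.

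**The plan's own figures.** 0.20 × 52 = 10.4, which agrees with the 10 expected remitters and leaves 52 − 10 = 42 others. On size, "the sample size was estimated as 10-13 patients per group", and "These calculations were based on a significant difference of sputum IL-5 obtained as preliminary results". The IL-5 difference and SD are not stated, so 10 to 13 cannot be reproduced from the plan's inputs. The pair is internally consistent: n per group = 2(z₀.₉₇₅ + z_power)²/d², rounded up, returns exactly 10 at 70% power and 13 at 80% for d between about 1.112 and 1.143. The sensitivity split below takes the upper figure: 13 against 39.

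**Why the level shifts.** Set the others' SD to 1 and the remitters' SD to r, with 10 and 42 patients.

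- True variance of the difference in means: r²/10 + 1/42.
- Expected pooled estimate of it: [(9r² + 41)/50] × (1/10 + 1/42).
- r = 1.5: true 0.225 + 0.0238 = 0.2488; pooled 1.225 × 0.1238 = 0.1517. The standard error is too small by a factor √(0.1517/0.2488) = 0.78. The critical value 2.009 then acts like 2.009 × 0.781 = 1.57, a two-sided normal tail of about 11.7%.
- r = 0.67: true 0.0449 + 0.0238 = 0.0687; pooled 0.9008 × 0.1238 = 0.1115. The factor is 1.27, the effective critical value 2.56, and the tail about 1.0%.

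This approximation ignores the sampling variation of the pooled SD. Simulation includes it.

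**Type I error at nominal 5%** (400,000 simulated datasets per case; numerical integration of the pooled-test rejection probability agrees within 0.2 points):

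| SD ratio | Student, 10 v 42 | Student, 13 v 39 | Student, 26 v 26 |
|---|---|---|---|
| 0.5 | 0.4% | 0.9% | 5.2% |
| 0.67 | 1.4% | 1.8% | 5.0% |
| 0.8 | 2.5% | 2.9% | 5.0% |
| 1 | 5.0% | 5.0% | 5.0% |
| 1.25 | 8.7% | 7.9% | 5.0% |
| 1.5 | 12.4% | 10.7% | 5.1% |
| 2 | 18.6% | 15.4% | 5.1% |

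The balanced column shows that the imbalance drives the problem. Welch's test, t = (difference in means)/√(s₁²/n₁ + s₂²/n₂) with Satterthwaite degrees of freedom, gives 5.0% to 5.2% at 10 v 42 and 5.0% to 5.1% at 13 v 39.

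**Price of Welch's test when the SDs are equal** (power, Student → Welch):

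| d | 10 v 42 | 13 v 39 |
|---|---|---|
| 0.8 | 60.6% → 56.1% | 68.7% → 66.1% |
| 1.0 | 79.5% → 74.9% | 86.5% → 84.4% |
| 1.2 | 91.6% → 88.3% | 95.7% → 94.4% |

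The loss is about 3 to 5 points at 10 v 42 and about 1 to 3 at 13 v 39. If remitters vary less, Welch gains: at r = 0.67 and a difference of one SD of the others, 10 v 42, power rises from 89.1% to 95.0%. If they vary more, Student's test shows higher nominal power (67.1% against 45.0% at r = 1.5), but it does so while rejecting 12.4% of true nulls.

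**The case against.** **No unequal spread is shown.** This stands. The documents give no group SDs, and at a ratio near 1 the error is near 5%. Remitters must meet every remission criterion while the others may fail any one. That makes unequal spread plausible but does not establish it.

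**Pooled variance is inferred.** The plan names the test but not its variance handling, and its proviso about appropriateness could cover an undescribed variance check. This also stands, so it cannot be said that a pooled test was certainly used for every variable. The text would still need the same clarification. A preliminary F test at 5% would not be enough: choosing between the two tests that way gives a type I error of 3.3% at ratio 0.67 and 8.6% at ratio 1.5 (10 v 42).

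**10 v 42 is the least favourable split.** The plan does give 10 as a minimum. But 20% of 52 is 10.4, so 10 is also close to its central expectation, and at 13 v 39 the distortion shrinks only slightly.

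**It does not touch the study question.** Correct. The aim concerns sputum mediators, none of which is on the normal list. On the plan's logic they go to Mann-Whitney, and the logistic regression and ROC analyses do not use the t test. Mann-Whitney also drifts when spreads differ at 10 v 42 (1.5% at ratio 0.5 and 11.2% at ratio 2, for normal data with equal centres), and Welch's test does nothing about that.

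**Welch's test is not free.** True at these sizes, and the price matters in a study planned for 70% to 80% power. A reader used to near-balanced groups, where the loss is negligible, might assume otherwise.

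**Conclusion.** The point holds as a cheap improvement. At the expected split, Student's t test is well off its nominal 5% in either direction once the SDs differ by about a quarter: 2.5% at a ratio of 0.8 and 8.7% at 1.25. The range is 1.4% to 18.6% for ratios of 0.67 to 2. Welch's test holds the level. This rests on normal data, an assumed SD ratio, roughly 10 remitters among 52, and the ordinary pooled-variance meaning of Student's test.

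A reader might infer two stronger conclusions that the documents do not support. One is that the baseline p-values are wrong by some known factor. The figures above are rejection rates under assumed ratios, not errors in any individual p-value. The other is that the findings on sputum mediators as predictors of remission are compromised. The affected analysis is only the baseline comparison of the normally distributed variables.

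**What to change.** In the Statistical analysis section, name Welch's unequal-variance t test for the variables found to be normally distributed, without a preliminary variance test. Report each difference in means with its Welch 95% interval, and show the group SDs so that readers can judge the spread.

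The cost is small but more than a change of wording. Recruitment ran from 2014 to 2021, the document is dated January 2023, and the tests are described in the past tense, so the t-test comparisons would have to be rerun. No new data are needed. The statistical price is the power loss shown above if the spreads turn out to be equal.

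### Must the plan test sputum mediators directly against blood eosinophils because the background says sputum has the better potential?

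*Combined protocol and SAP*

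**What the plan says.** Scientific Background and goal reports that, in earlier post-hoc trial analyses, "high blood eosinophil level was linked to a better improvement in terms of reduction of exacerbation rate". It then argues that "biomarkers reflecting local inflammation, such as those measured in induced sputum, have a better potential to predict the intensity of response to biologics", because sputum shows what is happening in the bronchi. The goal that closes the section is narrower: "The goal of this paper is to analyze the role of mediators of the T2 cascade in the sputum as predictors of remission". The aim under Study design repeats this and names no comparator.

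Statistical analysis describes chi-square or Fisher tests, t or Mann-Whitney tests, logistic regression and ROC curves. For the regression it states: "Univariate logistic regression was considered to model the association between patient remission status and demographic, clinical and biological variables". For the curves it states: "The p-values associated with the ROC curves tested the null hypothesis that the area under the curve equals 0.50". No test between two curves, no adjusted model and no added-value analysis is described. The sub-analyses listed under Patients change the outcome and name no comparator.

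On size, Study design says "we expected a sample size of at least 10 patients in the remission group", out of 52. The calculation behind it concerns a two-group difference in one mediator: "These calculations were based on a significant difference of sputum IL-5 obtained as preliminary results".

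**The concern.** A reader who takes the background at its word expects the study to show whether sputum does better than blood. Every planned null hypothesis is of no association: no group difference, odds ratio 1, or AUC 0.50. None is of no difference between markers. Blood eosinophils may well appear among the biological variables, so a table could show a mediator with p below 0.05 beside blood eosinophils with p above it. Reading that as proof that sputum is better is the familiar error of treating a difference in significance as a significant difference. With about 10 remitters the pattern can arise by chance when the two markers are equally good. At stake would be an unsupported claim that sputum induction is worth doing instead of, or on top of, a routine blood count.

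**Working it through.** **1. Rationale, goal and analysis side by side.**

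| Element | Content | Comparison with blood? |
|---|---|---|
| Background | sputum expected to predict intensity of response better than blood | yes, as rationale |
| Goal and aim | sputum mediators as predictors of remission | no |
| Sample size | two-group difference in sputum IL-5 | no |
| Analysis | single-marker tests against no association | no |

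Goal, sample size and analysis agree with each other. Only the background sentence goes further.

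**2. The plan's own figures.** The IL-5 difference and SD are not given, so 10-13 per group can only be back-solved. With two-sided 5% significance, d = (z for alpha + z for power) × √(2/n):
- n = 10, power 70%: (1.960 + 0.524) × √(2/10) = 1.11
- n = 13, power 80%: (1.960 + 0.842) × √(2/13) = 1.10

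Both ends fit one standardised difference near 1.1, which for normal scores is an AUC of Φ(1.1/√2) = 0.78. Expected remitters are 52 × 0.20 = 10.4, which matches the plan's figure of 10. None of this concerns a comparison of markers.

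**3. Is the feared misreading possible?** Assumptions, none from the documents: 10 remitters against 42 others, normal scores, the same true separation for mediator and blood, and mediator-blood correlation 0.3-0.7. Simulated frequency of the mediator being significant and blood not (exact Mann-Whitney, two-sided 0.05):

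| Common separation | Frequency |
|---|---|
| 0.3 SD | 7-9% |
| 0.5 SD | 11-16% |
| 0.8 SD | 13-20% |
| 1.1 SD | 8-11% |

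A repeat simulation agreed to within about 1.5 percentage points. By symmetry the reverse pattern (blood significant, mediator not) is equally frequent. So the pattern is possible, but it misleads only if someone draws the comparison from it.

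**4. What would a direct comparison deliver?** Take AUC 0.80 against 0.65, with 10 and 42 patients. The Hanley-McNeil standard errors are 0.089 and 0.103. With correlation 0.5 between the two estimates (assumed):
- SE of the difference = √(0.0888² + 0.1027² − 2 × 0.5 × 0.0888 × 0.1027) = 0.097
- 95% half-width = 1.96 × 0.0965 = 0.19
- power = Φ(0.15/0.0965 − 1.96) = 0.34
- difference detectable with 80% power = 2.80 × 0.0965 = 0.27

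Simulating the paired DeLong interval, with the mediator at 1.1 SD and each marker's direction fixed in advance:

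| Blood separation | True AUC gain | Power |
|---|---|---|
| 0.3 SD | 0.20 | 43-71% |
| 0.5 SD | 0.14 | 28-47% |
| 0.8 SD | 0.07 | 10-15% |

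Half-widths are about 0.13-0.23. A logistic model with one mediator and blood eosinophils would have 10/2 = 5 remissions per predictor.

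**5. Multiplicity.** Eleven mediators are listed under Sputum inflammatory mediators measurement. If all share blood's true AUC (0.5-1.1 SD, inter-mediator correlation 0.3-0.6, direction taken from the data), at least one unadjusted 95% interval favours a mediator in 11-22% of cohorts; a repeat run gave 9-21%. Bonferroni limits reduce this to 1-3%, at a further cost in power. These figures cover all eleven mediators, whereas those in step 3 are per mediator, so the two sets should not be compared.

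**The case for a change.** The best case for a change is that the background sets the reader up for a comparison, the tables may supply its raw material, and nothing in the plan warns against drawing it. For a single mediator, a paired AUC difference answers the question properly: with equal true AUCs its 95% interval wrongly favours the mediator in only 1-4% of simulated cohorts, against 7-20% for the contrast of p-values. Low power is a reason to show an interval, not to leave readers comparing two p-values. The cost would be small: one limiting sentence, or a few extra estimates.

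Much of this stands. The statistical point is right, and a claim that sputum beats or adds to blood could not rest on the planned analyses. It does not follow that the plan must change:

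- No section makes that claim or plans to. The harm depends on a guess about how the results will be written up.
- A sentence limiting the conclusions would alter no estimate, test or dataset.
- The extra comparison would be post hoc. Recruitment ran from 2014 to 2021, and the plan already reports distributional results ("normal distribution was found for age, BMI, ACQ").
- It needs a baseline blood eosinophil count. One is probably held, but Blood samples names only a leukocyte count, and the eosinophil criterion under Patients is post-treatment.
- That post-treatment count (below 300 cells/µl) is part of the remission definition, so a contrast with baseline blood eosinophils would be hard to interpret.

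**Conclusion.** The observation is correct: no comparison of sputum mediators with blood eosinophils is described, and none can be read off the planned tests. The concern does not hold as a fault in the plan, because the stated goal is prediction of remission by sputum mediators and the planned analyses address it, unadjusted. The background sentence explains why sputum was chosen.

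Adding the comparison would gain little here: half-widths of about 0.13-0.23 on the AUC scale, power from 43-71% if blood is weak down to 10-15% if it separates by 0.8 SD, and an 11-22% chance of at least one false favourable interval across 11 mediators without adjustment. These sizes rest on 10 remitters among 52, normal scores, and assumed separations and correlations; only the 52 patients, the roughly 10 remitters and the 11 mediators come from the documents. The judgement itself rests on the stated goal. It would differ if superiority or added value over blood eosinophils were an objective or a planned conclusion, and neither appears.
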